## 7.0 Risks.

All enrolled subjects will have a clinical diagnosis of congenital heart disease with sinus node dysfunction as defined in the inclusion criteria.

Supporting evidence for the clinical diagnosis will be reviewed by the principal investigator prior to enrollment. Patients with sinus node dysfunction are often more symptomatic and likely to experience adverse cardiovascular outcomes by nature of the disease. Those with pacemakers are at risk for lead malfunction and are other forms of pacemaker system malfunction. These risks are inherent to the patient population studied here.

There are risks associated with exercise testing in patients with ACHD, including the risk of provoking both atrial and ventricular arrhythmias. Nevertheless, exercise testing is routinely used to assess clinical status in the adult congenital heart disease population.

There are risks of loss of confidentiality related to the study procedures. Privacy issues are discussed in greater detail in section 11.0.

#### 8.0 Reporting of Adverse Events (AE) or Unanticipated Problems involving Risk to Participants or Others

AES will be reported to the IRB according to the IRB policies and procedures.

#### 9.0 Study Withdrawal/Discontinuation

Subjects may withdraw from the study at any time. Subjects will be unblinded at the time of withdrawal.

#### 10.0 Statistical Considerations

##### Sample Size Estimation and Power Analysis

The primary endpoint of this randomized controlled 2x2 cross-over trial will be to measure the influence of autonomic function on heart rate response, and to show an equivalent response for both epicardial and transvenous CLS pacemaker systems. The objective of this study is to evaluate changes in heart rate in response to the CLS algorithm versus a standard accelerometer during various tests of autonomic function. Previous studies of adults with chronotropic incompetence using the CLS algorithm have demonstrated a mean increase in heart rate of  $16.1 \pm 1.1$  beats/minute during mental stress with CLS-on versus  $5.8 \pm 0.6$  beats/minute with standard accelerometer ( $p<0.001$ ).

A further pilot study using ANSAR demonstrated a mean increase in 12.5 beats/minute during isometric hand-grip with CLS-on versus 2.9 beats/min with standard accelerometer ( $p=0.004$ ), 13.2 beats/minute during deep breathing versus 2.9 beats/minute ( $p=0.004$ ), 16.0 beats/minute during Valsalva maneuver versus 4.5 beats/minute ( $p=0.004$ ), and 14.9 beats/minute for postural change versus 6.2 beats/minute ( $p=0.039$ ). The results of the prior pilot study are summarized below.

ANSAR HEART RATE	Baseline	DOD-CLS	DDD	T test	Wilcoxon test
Resting	55.8	70.0	60.8	<0.001	0.004
Isometric Handgrip	59.4	71.9	62.3	<0.001	0.004
Deep Breathing	58.0	71.2	60.9	<0.001	0.004
Valsalva maneuver	57.1	73.1	61.6	<0.001	0.004
Postural Change	58.1	73.0	64.3	0.015	0.039

From Pavri et al. Circulation 2006;114;II 749. 

A two-sided t-test achieves 80% power to infer that the mean difference is not 0 when the total sample size of a cross-over design is 40 (or 81% when n=24 and 96% when n=30) assuming a 5% type I error. The actual difference and the square root of the within mean square error are assumed to be 10. Considering a drop-out rate of 30%, a total of 57 patients will need to be enrolled to achieve the target sample number.

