## 2.0 Rationale and Specific Aims

Improvement in sensor-based rate adaptation for sinus node dysfunction is needed in the CHD population. Emerging data suggest that greater aerobic capacity and heart rate

reserve are independently associated with superior outcomes in this population. Improvements in these parameters can be expected with the use of the Biotronik CLS algorithm and this pacing system may therefore be particularly well-suited to patients with CHD.

The Specific Aims of this protocol are:

Primary Aim: To determine the performance of CLS for CHD patients after both transvenous and epicardial pacemaker implantation

Hypothesis: CLS after either pacemaker implantation strategy will result in equivalent improvements in autonomic control of chronotropic response as compared to standard sensor based rate modulation

Primary outcome: Objective change in autonomic modulation of heart rate while randomized to CLS pacing with mental stress and ANSAR testing

Secondary outcomes: Increase in aerobic capacity, non-sedentary behavior, and quality of life while randomized to CLS pacing

This will be a single-blind (blinded subjects) randomized cross-over study, in which each patient will receive treatment A (CLS-on or CLS-off) for 3 months followed by treatment B (CLS-0ff or CLS-on).

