### 4.0 Inclusion/Exclusion Criteria

Inclusion criteria:

- o Congenital heart disease
- o Simple, moderate, or complex congenital heart disease
- o Adolescent or adult age group (age >14 and <65 years)
- o Significant sinus node dysfunction
- o Atrial pacing percentage >70%

- o Intrinsic dysfunction resulting from congenital lesion or cardiac surgery •
- Secondary sinus node dysfunction due to antiarrhythmic drug therapy
- o Existing, fully functional Biotronik pacemaker or ICD with CLS capability
- o Epicardial or transvenous route of pacemaker implantation

Exclusion criteria:

- o Unable to complete cardiopulmonary exercise testing (CPET) o
- Contraindication to CPET
- o Decreased mental capacity or known psychiatric disorder
- o Congestive heart failure, NY HA class IV
- o Total atrial tachyarrhythmia burden >20%

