## 5.0 Enrollment]Randomization

Patient Enrollment: The treating physician will identify potential subjects with a previously implanted Biotronik pacemaker and present a brief overview of the study; if the subject is interested, the study will be described in detail. Informed consent will be obtained by the investigator after discussing the study, including the voluntary nature of participation and notification the subject can withdraw at any time. Ample time for questions and answers will be allowed. The investigator will give the subject and his/her legal guardian the opportunity to take the consent home to think about it more, with the option to call or meet with the investigator to ask additional questions. If the subject and/or his/her parent/legal guardian agree to participate, the investigator will ask them to sign a written, informed consent and assent. A copy of the assent and consent will be given to the subject and/or his/her parent/legal guardian.

Randomization Procedure: This will be a single-blind placebo-controlled randomized crossover study with 2 treatments: CLS-on versus CLS-off (accelerometer only). Each enrolled patient will receive both treatments for 3 months. The order of treatments will be randomized 1 :1.

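### Equivalence of CLS response between epicardial and transvenous systems is part of the primary endpoint, but the visible plan gives no margin, equivalence rule, numbers per route or power for it

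*Combined protocol and SAP*

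**What the plan says.** Under Sample Size Estimation and Power Analysis (section 10.0), the primary endpoint has two parts: to measure autonomic influence on heart rate response, and "to show an equivalent response for both epicardial and transvenous CLS pacemaker systems". The hypothesis in section 2.0 agrees: "CLS after either pacemaker implantation strategy will result in equivalent improvements in autonomic control of chronotropic response", relative to standard sensor-based pacing.

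Other statements of the objective leave route out. The primary outcome in section 2.0 is "Objective change in autonomic modulation of heart rate while randomized to CLS pacing with mental stress and ANSAR testing", which names neither route nor a comparator. The next sentence of section 10.0 gives the objective as "to evaluate changes in heart rate in response to the CLS algorithm versus a standard accelerometer during various tests of autonomic function"; it names the accelerometer but not route.

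The power statement concerns a two-sided cross-over t-test "to infer that the mean difference is not 0", with a difference of 10 and a root within mean square error of 10. The Statistical Analysis Plan in section 10.0 names ANOVA or Kruskal-Wallis for differences between group means, with p-values and 95% confidence intervals. It does not say which groups are meant.

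On design, eligibility in section 4.0 is "Epicardial or transvenous route of pacemaker implantation", with no quota. In section 5.0, "The order of treatments will be randomized", and section 6.0 describes the same allocation. Blinding covers subjects only: "This will be a single-blind (blinded subjects) randomized cross-over study".

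**The concern.** A claim of equivalence needs a margin that says how large a difference is tolerable, and a rule that concludes equivalence only when the data exclude anything larger. The visible plan has neither. The only inferential tools it names test for a difference, so the only route to the word equivalent that it offers is a non-significant result. Such a result can come from too few patients as easily as from true similarity.

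The cross-over does not rescue the comparison. Each patient has one route, fixed before enrolment, so route is compared between patients. It gains neither the protection of randomisation nor the within-patient precision of the on-off contrast. Epicardial and transvenous patients may differ in other ways that affect heart rate response.

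Route is the distinctive question here: the title names epicardial implantation, and section 3.0 says that epicardial CLS data are essentially isolated case reports. At stake is whether the trial could report that epicardial CLS works as well as transvenous CLS on evidence that would not exclude a substantial loss.

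**Working it through.** **Inputs.** From section 10.0: assumed CLS effect 10 bpm, root within mean square error 10, target 40 completers, 5% type I error. Assumptions: the route split is not stated, so 20/20 is used, with 10/30 as a less even case. The SD of a patient's on-off difference is √2 × 10 = 14.1 if the stated 10 is the within-patient root MSE, or 10 if it is the SD of the difference. Results are given for 14.1, with 10 in brackets.

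**1. The plan's own power figures.** For the on-off contrast, SE = 10 × √(2/N) with N − 2 degrees of freedom. Two-sided 5% power for 10 bpm is 91% at N = 24 (stated 81%), 96% at N = 30 (stated 96%) and 99% at N = 40 (stated 80%). Only the N = 30 figure is reproduced. That mismatch is a separate issue; what matters here is that none of the three figures concerns route.

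**2. Precision of the route contrast.** Compare the mean on-off difference between routes: SE = SD × √(1/n₁ + 1/n₂), 38 degrees of freedom (adjusting for period costs one more). At 20/20, √(1/20 + 1/20) = 0.316, so SE = 4.47 (3.16) bpm. The 90% CI half-width is 1.686 × SE = 7.5 (5.3) bpm.

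**3. What a difference test would miss.** Suppose one route loses 5 bpm, half the assumed effect. The noncentrality is 5/4.47 = 1.12 (5/3.16 = 1.58), and the two-sided 5% critical value is 2.02. The result is non-significant 81% (66%) of the time at 20/20, and 84% (73%) at 10/30.

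**4. What an equivalence test would achieve.** Two one-sided 5% tests with a true route difference of 0 declare equivalence when |estimate| + 1.686 × estimated SE is below the margin.

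| Quantity, 40 completers | SD 14.1 | SD 10 |
|---|---|---|
| Power, margin 5 bpm, 20/20 | about 0% | 3% |
| Power, margin 10 bpm, 20/20 | 42% | 86% |
| Margin giving 80% power, 20/20 | 13.3 bpm | 9.4 bpm |
| Margin giving 80% power, 10/30 | 15.4 bpm | 10.9 bpm |

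The margins in the first two rows are illustrations; the documents give none. A margin of 10 bpm equals the whole assumed CLS effect.

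**5. How far the SD is known.** The documents do not settle it. The pilot table gives p-values but no n, and several entries are only bounds (<0.001), so they cap an SD for an assumed n without giving a lower limit. The mental stress results (16.1 ± 1.1 versus 5.8 ± 0.6) do not say what the ± is. If it were an SD, the SD of the difference would be at most 1.1 + 0.6 = 1.7 bpm; if a standard error, the SD cannot be recovered without n. Steps 3 and 4 are therefore conditional on the planning value.

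**The case against.** The strongest reply is that the powered and randomised question is CLS against the accelerometer, and that equivalent is used loosely to mean that CLS works with either route. The primary outcome in section 2.0 and the objective sentence in section 10.0 both omit route, which fits that reading. What stands is that the documents are not consistent. But the word is in both the primary endpoint sentence and the hypothesis, so if it is informal it should be changed.

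A second reply is that variability may be well below the planning value. This also stands: with an SD of 4.0, for example, a 5 bpm loss would be missed only about 3% of the time at 20/20. A reader might infer from the table above that the trial is too small to show equivalence; the documents do not support that, because they do not fix the SD. A small SD still would not supply a margin or a rule.

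A third reply is that the plan already promises 95% CIs, and that a 95% CI lying inside a margin is a valid, conservative equivalence rule. True, but no margin is stated.

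Finally, a figure in section 6.0 is not shown, so the point is limited to the visible text. The sample size and analysis text, where a margin and a test would normally appear, is present.

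**Conclusion.** The point holds, and should be fixed before analysis. Part of the stated primary endpoint has no valid rule by which it could succeed or fail, and the analysis named cannot support the claim made. This follows from the text alone and rests on no assumed SD.

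The numerical size is conditional on 40 completers, the assumed splits and the planning SD of 14.1 (10). Under those, a non-significant route difference would be weak evidence: a loss of half the CLS effect would be missed 81% (66%) of the time at 20/20.

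Two stronger readings go too far. A reader might infer that the sponsor intends to declare equivalence from a non-significant p-value; the analysis section does not say so, nor even that its groups are routes. A reader might also infer that the trial's main comparison fails; the missing route rule does not touch the randomised CLS-on versus CLS-off contrast.

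**What to change.** Amend sections 2.0 and 10.0 (including the Statistical Analysis Plan) in one of two ways.

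**(a) Route as an estimate.** Make CLS-on versus CLS-off the primary claim. Report the mode-by-route difference in within-patient on-off change, adjusted for period, with its CI, labelled as non-randomised. State that a non-significant difference is not evidence of equivalence. Drop the word equivalent unless the CI lies inside a justified margin, fixed before anyone on the study team has seen outcome data by mode and route; this timing matters because only subjects are blinded.

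**(b) Equivalence kept as a primary claim.** Name one response and justify a margin for it in bpm, fixed at the same time as in (a). Use two one-sided 5% tests (a 90% CI inside the margin) or the more conservative 95% CI already planned. Keep the non-randomised label. State expected completers per route, the SD relied on, and the power that the planned size actually gives.

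**Cost.** Both are changes of text, with no new visits or data, but neither is free. Under (a), a stated primary claim becomes an estimate with its CI. Under (b), the stated equivalence power may be low. If the sponsor wanted 80% power with equal routes and no true difference, a 5 bpm margin would need about 138 (70) completers per route at SD 14.1 (10), and a 10 bpm margin about 35 (18), against 40 planned in total. A smaller, documented SD would reduce these numbers.

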## Randomization

[figure not shown]
There will be a 50:50 randomization, with half the subjects randomized to CLS-on then CLS-off, and half randomized to CLS-off then CLS-on.

Subjects previously receiving rate-responsive pacing with CLS that are randomly selected to CLS-on will continue with the identical programmed parameters. For subjects not previously receiving rate-responsive pacing with CLS that are randomly selected to CLS-on nominal programming will be utilized with a base rate of 60 beats per minute.

Subjects will then initiate treatment A (CLS-on or CLS-off) in a blinded fashion. During the testing period, subjects will be tracked with the implanted device accelerometer to quantify physical activity. At 3 months, all subjects will undergo testing as noted below.

- 24 hour Holter monitoring with spectral analysis
- Cycle-ergometer stress with cardiopulmonary gas exchange analysis
- Free form activities with cardiopulmonary gas exchange analysis (staircase, walking, sweeping, suitcase lifting with right and left arms, etc.)
- ANSAR testing (hand grip, Valsalva, deep breathing, and orthostatic challenge)
- Mental stress test with continuous electrocardiographic recording
- Quality of life questionnaire (SF-36/Somerville index)

After 3 months of treatment A, subjects will be reprogrammed to treatment B. Tracking of physical activity with the device accelerometer will continue during this period. After 3 months of treatment B, repeat testing will be repeated as described above. At the conclusion of the study, patients will be asked which pacing mode is preferred.

Patients will be followed during both treatment phases per usual clinical routine. Patients who experience significant symptoms (extreme fatigue, debilitating palpitations, or other clinically relevant symptoms) will be evaluated by their treating physician. Subjects that have any adverse events during treatment A will discontinue treatment A and immediately crossover to treatment B. Subjects with events during treatment B will be removed from the study and unblinded. Further treatment will be determined by the treating physician.

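### The ANSAR pilot increases are not rises from rest: 9.2 of the mean 10.0 bpm CLS-DDD gap is already present at rest, and the trial does not say what its primary heart-rate change is measured from

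*Combined protocol and SAP*

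**What the plan says.** Section 2.0 gives the primary outcome as "Objective change in autonomic modulation of heart rate while randomized to CLS pacing with mental stress and ANSAR testing". Section 10.0 puts the primary endpoint as being to "measure the influence of autonomic function on heart rate response, and to show an equivalent response for both epicardial and transvenous CLS pacemaker systems", and the objective as being to "evaluate changes in heart rate in response to the CLS algorithm versus a standard accelerometer during various tests of autonomic function". None of these sentences says what the change is measured from. The Statistical Analysis Plan paragraph, which names ANOVA or Kruskal-Wallis for group means, does not say either.

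For planning, section 10.0 cites a mental-stress study (16.1 v 5.8 bpm) and an ANSAR pilot. The pilot is reported as a "mean increase in 12.5 beats/minute during isometric hand-grip with CLS-on versus 2.9 beats/min with standard accelerometer", with matching pairs for deep breathing (13.2 v 2.9), Valsalva (16.0 v 4.5) and postural change (14.9 v 6.2). A table follows, introduced by "The results of the prior pilot study are summarized below". It has a Resting row that the text does not mention. The power statement then says: "The actual difference and the square root of the within mean square error are assumed to be 10".

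Under Randomization in section 6.0, prior CLS users assigned to CLS-on "will continue with the identical programmed parameters". For other subjects assigned to CLS-on, "nominal programming will be utilized with a base rate of 60 beats per minute". The visible text gives no base rate for CLS-off. ANSAR and mental stress testing are listed after each treatment period and are absent from the baseline list. One figure in this part is not shown.

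**The concern.** A response to an autonomic test is the rate during the test compared with the rate just before it, under the same pacing mode. If one mode paces faster at rest, a difference in rate during the test can arise without any difference in response. The pilot text describes its figures as increases during the tests, yet the table's Resting row shows CLS well above DDD with no stressor applied.

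Two things are at stake. The first is whether the ANSAR pilot supports a planning difference of 10 bpm in response. The second, which matters more, is what a positive primary result would mean. Randomisation and crossover do not remove a resting-rate difference, because it is itself an effect of the mode. With no reference state fixed in advance, the primary analysis could show either autonomic response or only a faster resting rate. A rest reading that was never taken cannot be recovered later.

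**Working it through.** **Inputs.** Pilot table in section 10.0, in bpm (Baseline / CLS / DDD): rest 55.8 / 70.0 / 60.8; hand-grip 59.4 / 71.9 / 62.3; deep breathing 58.0 / 71.2 / 60.9; Valsalva 57.1 / 73.1 / 61.6; postural change 58.1 / 73.0 / 64.3. Planning values from the same section: N=40, difference 10, within-subject root mean square error 10, two-sided 5%.

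**Step 1: reproduce the quoted increases.** Mode minus same-row Baseline gives, for hand-grip, 71.9 - 59.4 = 12.5 and 62.3 - 59.4 = 2.9. All eight figures in the text reproduce exactly this way. The same subtraction in the Resting row gives 70.0 - 55.8 = 14.2 and 60.8 - 55.8 = 5.0, which is an increase with no test being done.

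**Step 2: measure from each mode's own rest** (CLS minus 70.0; DDD minus 60.8).

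| Row | CLS - DDD | CLS rise | DDD rise | Net of rest | 9.2 as share of gap |
|---|---|---|---|---|---|
| Rest | 9.2 | – | – | – | – |
| Hand-grip | 9.6 | 1.9 | 1.5 | +0.4 | 96% |
| Deep breathing | 10.3 | 1.2 | 0.1 | +1.1 | 89% |
| Valsalva | 11.5 | 3.1 | 0.8 | +2.3 | 80% |
| Postural change | 8.7 | 3.0 | 3.5 | -0.5 | 106% |

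Mean gap during the manoeuvres: (9.6 + 10.3 + 11.5 + 8.7)/4 = 10.025. Resting share: 9.2/10.025 = 92%. Mean net of rest: (0.4 + 1.1 + 2.3 - 0.5)/4 = +0.825. The meaning of Baseline does not affect these contrasts, because one Baseline value serves both modes and cancels from CLS minus DDD. The table's own tests agree: the Resting row has the same p-values (<0.001 and 0.004) as hand-grip, deep breathing and Valsalva.

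**Step 3: source of the assumed 10.** The ANSAR mean gap (10.0) and the mental-stress gap (16.1 - 5.8 = 10.3) both fit. No resting rates are given for mental stress, so that source cannot be checked in the same way.

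**Step 4: what a resting gap alone could do in this trial.** For a 2x2 crossover, SE = s × sqrt(2/N) with N - 2 degrees of freedom, and the probability of significance comes from the noncentral t distribution. At s = 10 and N = 40, SE = 10 × sqrt(2/40) = 2.236 and t(38) = 2.024, so the critical difference is 4.53 bpm.

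The plan's inputs conflict. A difference of 10 with s = 10 at N = 40 gives 99% power, not the stated 80%. Keeping 80%, N = 40 and the difference of 10 implies s of about 15.6. Then SE = 15.6 × sqrt(2/40) = 3.488 and the critical difference is 2.024 × 3.488 = 7.06 bpm. Both readings are shown.

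| Assumed resting gap, no added response | s = 10 | s = 15.6 |
|---|---|---|
| 9.2 bpm (the pilot's) | 98% | 73% |
| 6.43 bpm | 80% | 44% |
| 5 bpm | 59% | 29% |
| 3 bpm | 26% | 13% |

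All four gaps are assumptions for this trial. The documents give no resting rates by mode for its population.

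**The case against.** The strongest reply has four parts.

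- **The pilot breakdown is imprecise.** There is no n or SD, Baseline is undefined, and the text does not say whether rates are means or peaks, or that the single Resting row is the pre-test state for each manoeuvre. The column reads DDD where the text says standard accelerometer, so the comparator is uncertain. This stands. The net values are point estimates only, and a reader should not infer that CLS adds no autonomic response.
- **The 10 bpm may come from mental stress**, which the primary outcome names first. This stands. A reader might infer that the planning difference is wrong or the trial underpowered. The documents do not support that: the mental-stress source cannot be checked, and no SD is given for a rest-referenced outcome.
- **The pilot's calculation may not be possible in this trial.** The visible schedule has no common Baseline ANSAR reading. This also stands, and it leaves rate during the test as the realistic route to the problem. The mode contrast is the same either way, since a shared Baseline cancels.
- **The objective can be read as a simple between-mode contrast during testing, and a faster resting rate may be a genuine CLS effect.** Both are possible. But section 2.0 names autonomic modulation as the outcome, and resting rate is a different quantity that should carry its own label.

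A reader might also infer that the epicardial v transvenous comparison is biased. A resting offset of equal size in both routes cancels there. It matters only if it differs by route, and the documents give no data by route.

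**Conclusion.** The concern holds as stated in the heading. By exact arithmetic on the plan's own table, the quoted ANSAR increases are not responses to the manoeuvres, and 92% of the mean mode gap is present at rest. The ANSAR pilot therefore does not support a 10 bpm difference in response; the mental-stress support for that figure is neither confirmed nor refuted.

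The trial leaves the reference for its primary heart-rate change undefined, and its only worked example of an increase would count resting rate as response. How much this matters depends on the resting gap in this trial, which is unknown, and on which of the plan's two conflicting SD readings applies. Over assumed gaps of 3 to 9.2 bpm, the chance of a significant result with no added response is 26% to 98% at an SD of 10, and 13% to 73% at about 15.6. The definition should be settled before any data are analysed, because it decides what a positive result means.

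**What to change.** 1. Define the primary response, for ANSAR and mental stress alike, as rate during the test minus rate at rest in the same session and mode, compared CLS-on v CLS-off. Rate during the test adjusted for that rest value is an acceptable alternative; choose one in advance.
2. Use the same definition for the epicardial v transvenous comparison.
3. Report resting rate and rate during the test by mode, separately and labelled as such.
4. Take the rest value from a short pre-test recording, or from the continuous ECG already planned for mental stress.
5. Correct the pilot paragraph: name the same-row Baseline column as the reference, state the 9.2 bpm resting gap, and reconcile the DDD column label with the text.
6. State the source and scale of the assumed difference and SD of 10, and restate both if they are not rest-referenced. Reconcile them with the stated power.

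The cost is mainly protocol and SAP wording, plus at most a few minutes of rest recording per session. The real downside is a less favourable expectation for the ANSAR tests.

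### Section 10.0 states 80% power at n=40 but 96% at n=30 on one set of inputs, so the target of 40 completers does not follow from them

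*Combined protocol and SAP*

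**What the plan says.** All the figures are in section 10.0 of the combined protocol and SAP, under Sample Size Estimation and Power Analysis. The design is a 2x2 cross-over with 1:1 allocation to treatment order. The paragraph opens "A two-sided t-test achieves 80% power to infer that the mean difference is not 0" and attaches that power to a "total sample size of a cross-over design is 40 (or 81% when n=24 and 96% when n=30"), at a 5% type I error. The inputs follow: "The actual difference and the square root of the within mean square error are assumed to be 10". The target is then inflated: "Considering a drop-out rate of 30%, a total of 57 patients will need to be enrolled". No second set of inputs is given for any of the three pairs of sample size and power.

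The same section cites earlier CLS-on versus accelerometer results in support of the difference. The smallest contrast is "14.9 beats/minute for postural change versus 6.2 beats/minute" and the largest is "16.0 beats/minute during Valsalva maneuver versus 4.5 beats/minute". No source is given for the root within mean square error of 10.

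**The concern.** With the test, the alpha, the difference and the variance all fixed, power can only increase with the number of patients. The paragraph has it lower at 40 than at 24 or at 30. At least one stated power, or one stated input, must be wrong, and the pair in question is the one that sets the target of 40 and, through it, the enrolment of 57.

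The two ways of resolving the conflict describe different trials. If the inputs are right, 40 is more than twice the number needed for 80% power, and no other reason for 40 is given. If 40 is right for 80% power under a larger within-patient variance, the powers quoted at 24 and 30 are far too high. Because the plan expects 30% drop-out, a reader could then wrongly conclude that a shortfall in completers would cost little.

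**Working it through.** **Inputs (section 10.0).** Two-sided test, alpha 0.05; difference d = 10 bpm; root within mean square error Sw = 10; N = total completers, split equally between the two sequences; drop-out 30%.

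**Formula.** For a 2x2 cross-over, SE = Sw × √(2/N), the noncentrality parameter is d/SE, and df = N − 2. Power is the probability that a noncentral t exceeds the two-sided 5% critical value.

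**Power on the stated inputs**

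| N | SE | Noncentrality | Critical t | Power | Stated |
|---|---|---|---|---|---|
| 18 | 3.33 | 3.00 | 2.120 | 80.4% | – |
| 24 | 2.89 | 3.46 | 2.074 | 91.1% | 81% |
| 30 | 2.58 | 3.87 | 2.048 | 96.2% | 96% |
| 40 | 2.24 | 4.47 | 2.024 | 99.2% | 80% |

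The n=30 figure reproduces, which suggests that this is the formula and input set used there. The n=40 figure is off by 19 points and the n=24 figure by 10 points. At N = 17 power is 77.8%, so 18 is the smallest number that reaches 80%.

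**Could a misread digit explain it?** The 81% may be a misprint or text-extraction error for 91%, which is the computed value, so the argument does not rely on it. The 40 is confirmed by the next step of the plan: 40/0.70 = 57.1, against the stated 57 (57 × 0.70 = 39.9). For the 80% to be a misreading, the intended figure would have to be about 99%.

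**Could another method explain it?** None of the other readings tried gives 80% at N = 40 with alpha 5%:

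- normal approximation: 99.4%
- one-sided test: 99.7%
- SD of paired differences equal to 10: essentially 100%
- N read as patients per sequence: essentially 100%
- two parallel groups, N in total: 65%, 75% and 87% at 24, 30 and 40

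An alpha of 0.001 gives 80.5% at 40, but it contradicts the stated 5% and gives only 58.3% at 30. In any case, no reading with fixed inputs makes power fall as N rises.

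**What the stated powers would need.** Solving for Sw at d = 10:

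- 80% at N = 40 needs Sw = 15.6.
- 96% at N = 30 needs Sw = 10.1, which is 10 within rounding (95.5% to 96.5% corresponds to 10.2 to 9.9).
- 81% at N = 24 needs Sw = 11.7; if 91% was meant, Sw is about 10.0.

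The firm conflict is therefore between about 10 and 15.6. With Sw = 15.6, power is 57% at 24, 67% at 30 and 80% at 40.

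**What 40 completers would detect.** With Sw = 10 and N = 40, 80% power corresponds to d = 6.4 bpm. The cited CLS-on minus accelerometer differences are:

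- mental stress: 16.1 − 5.8 = 10.3
- handgrip: 12.5 − 2.9 = 9.6
- deep breathing: 13.2 − 2.9 = 10.3
- Valsalva: 16.0 − 4.5 = 11.5
- postural change: 14.9 − 6.2 = 8.7

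They are in line with the assumed 10, and all exceed 6.4.

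**The case against.** The strongest reply is that the contradiction is real but does little harm. On the only inputs in the plan the error is in the safe direction: 40 completers give 99% power, and even 24 (a loss of 33/57 = 58%) would keep 91%. The n=30 figure reproduces at 10 and 10, and so would n=24 if 91% was meant, so the 80%/40 pair may be the only slip. The value 15.6 appears nowhere in the plan; it is back-solved from the disputed 80%. The pilot table also points to a smaller variance. If its t-tests are paired CLS versus DDD comparisons and the pilot had about 9 patients, the postural-change row (8.7 bpm, p=0.015) implies a root mean square error near 6.0, and 5.4 to 7.4 for 8 to 12 patients. All are below 10.

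Much of this stands. On the stated inputs the trial is not underpowered, and 15.6 serves only as an illustration. The pilot argument rests on an assumed pilot size and on an assumed reading of the table, so it cannot settle which input was used. None of it explains how 80% at 40 was obtained.

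Two further points are fair. Restating the powers does not by itself say why 40 was chosen when 18 would give 80%. And 57.1 rounds up to 58, which is trivial.

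**Conclusion.** The concern holds. The power statement that sets the sample size is wrong as written: on the stated inputs, power at 40 completers is 99.2%, not 80%, and 80% is reached at 18. At 30% drop-out, 18 completers correspond to 18/0.70 = 25.7, or 26 enrolled, against the planned 57.

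This rests on the standard 2x2 cross-over t-test with equal sequences and N − 2 degrees of freedom, the method under which the plan's own n=30 figure reproduces. The contradiction between n=30 and n=40 needs no calculation. The documents do not show whether the 80% or one of the inputs is at fault, so the loss of power under a larger variance is a possibility and not a finding. The point should be corrected before the sample size justification is relied on.

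**What to change.** State which inputs produced 40 and make the paragraph agree with them.

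- **If 10 and 10 are the intended inputs:** restate the powers as 91% at 24, 96% at 30 and 99% at 40 completers. Say that 40 completers give 80% power for about 6.4 bpm, and give the reason for choosing 40, since 18 would reach 80% for 10 bpm. This rewords one paragraph and changes neither the design nor the patient number.
- **If 40 came from other inputs:** state them with their source and recompute all three powers. With a root mean square error of 15.6, for example, they would be 57%, 67% and 80%. The cost is recovering and documenting the inputs actually used; 40 and 57 stand if those inputs do give 80%.

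In either case, give a source for the root within mean square error. The step from 40 to 57 can stay as long as 40 does.
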